2.2.2 Exploratory Endpoints

- Frequency of VMS, which is the average daily frequency of moderate to severe VMS, defined as the sum of the number of moderate to severe VMS during 1 week divided by number of days with data.
- Severity of VMS, which is the average daily severity score of mild to severe VMS. Baseline VMS severity score is defined as $(2xFmo + 3xFse)/(Fmo + Fse)$, and VMS severity score for a specific week during the open label treatment period is defined as $(1xFmi + 2xFmo + 3xFse)/(Fmi + Fmo + Fse)$, where Fmi, Fmo, and Fse are the daily frequencies of mild, moderate, and severe VMS, respectively, during each applicable study week.
- MENQOL.

3 STUDY DESIGN

3.1 Overall study design

Study MT-8554-A02 is an open-label, long-term safety extension trial of Study MT-8554-01. The study will be initiated during the conduct of Study MT-8554-A01.

[figure not shown]
Subjects who complete the preceding trial (Study MT-8554-A01) and comply with eligibility criteria for Study MT-8554-A02 will be enrolled in a 52-week open-label treatment period. Visit 7 (Week 12) of Study MT-8554-A01 will be considered Visit 1 of Study MT-8554-A02. Assessments already carried out at Visit 7 (Week 12) of Study MT-8554-A01 will not be repeated. During the 52-week open-label treatment period, subjects will attend visits every 8 weeks between Visits 1 and 3 (Weeks 12, 20, and 28) and every 12 weeks between Visits 3 and 6 (Weeks 28, 40, 52, and 64).

All enrolled subjects will receive MT-8554 (was 10 mg initially, switched to 5 mg*) for 52 weeks. Study drug will be administered once daily before bedtime.

An End of Study (EOS) Follow-up visit will be conducted by phone for safety follow-up 30 days after the end of the open-label treatment period (see Figure 1).

*Note: Based upon the results of Study MT-8554-A01, the dose is changed from 10 mg to 5 mg because participating subjects will no longer derive potential clinical benefit from receiving 10 mg dose. All participating subjects who reconsent to continue the study will receive MT-8554 5 mg.

Figure 1 Study Design Schematic

3.2 Rationale for study design and treatment regimens

The objectives of this study are to obtain long term safety and tolerability data for MT-8554 when administered once daily before bed time in postmenopausal women with moderate to severe VMS who completed Study MT-8554-A01 according to the ICH-E1 guideline.

3.2.1 Risk:benefit statement

[REDACTED]

[REDACTED]

[REDACTED]

[REDACTED]

The Sponsor will undertake all reasonable measures, including thorough screening and safety monitoring procedures, to minimize the risk to subjects.

[REDACTED]

Additionally, subjects will receive no further dosing if they meet any of the withdrawal criteria listed in Section 4.5.

3.3 Rationale for dose selection

The primary objective of this study is to assess long-term safety and tolerability of MT-8554.

[REDACTED]

[REDACTED]

[REDACTED]

In the preceding study (Study MT-8554-A01), 5 mg was chosen as the medium dose, 1 mg was selected as a low dose to seek a minimal efficacious dose, and 10 mg/day as a high dose to seek a maximum efficacious dose.

All subjects entering in the study were initially allocated to 10 mg of MT-8554 for a further 52 weeks.

Based upon the results of Study MT-8554-A01 (Section 1.4), the dose is changed from 10 mg to 5 mg because participating subjects will no longer derive potential clinical benefit from receiving 10 mg dose. All participating subjects who reconsent to continue the study will receive MT-8554 5 mg.

4 SELECTION AND WITHDRAWAL OF SUBJECTS

The Sponsor does not operate a protocol waiver system for eligibility criteria.

4.1 Number of subjects

It is planned to enroll up to 364 subjects who have completed Study MT-8554-A01. The study will be finished when approximately 100 subjects complete a 52-week open-label treatment period and 30-day follow-up.

4.2 Recruitment methods

This study will enroll subjects who complete Study MT-8554-A01 and comply with eligibility criteria.

4.3 Inclusion criteria

A subject will be eligible for enrollment in the study if ALL of the following criteria apply:

1. Signed informed consent to participate in this study.
2. Subjects who complete Study MT-8554-A01 through Week 12.
3. In the Investigator's opinion, subject is able to understand the nature of the study, any risks involved in participation, and is willing to cooperate and comply with the protocol restrictions and requirements including transvaginal ultrasound and endometrial biopsy.

4.4 Exclusion criteria

A subject will NOT be eligible for this study if the subject meets the withdrawal criteria for Study MT-8554-A01.

4.5 Withdrawal of individual subjects

4.5.1 Discontinuation from treatment

Investigators may choose to temporarily or permanently discontinue study treatment for any reason, including AEs or tolerability.

If any clinically significant abnormality is detected on the clinical breast exam (see Section 6.5.2) at baseline or anytime during the study or there is any occurrence of unexplained uterine bleeding, study medication should be discontinued and subject should be referred to the specialists for further investigations per current standards. If all the required investigations such as physical examination of the breast, imaging and pathology are negative and available within 6 weeks, subject can resume study medication.

An unscheduled study visit can be used to reassess subject's symptoms and willingness to resume study drug.

If treatment is discontinued and the subject is not willing to resume study medication, every effort should be made to continue the subject on study, e.g., attending study visits and carrying out study procedures through to the final visit. For subjects declining to continue on the study, see Section 4.5.2.

The Suspension interval (start and end dates of suspension) and reason for suspending treatment must be recorded in source documents and the electronic Data Collection Form (eCRF).

Subjects who become pregnant during the study should be withdrawn from study treatment. Also see Section 8.8 for necessary documentation and procedures for following up with the subject.

4.5.2 Discontinuation from study

Subjects may withdraw from the study for any reason. The Investigator will discontinue a subject from the study if ANY of the following criteria are met:

- The subject wishes to voluntarily withdraw from the study
- The subject is lost to follow-up
- The subject is diagnosed with breast cancer
- The subject experiences elevated ALT or AST $>3 \times$ ULN and a total bilirubin $>2 \times$ ULN (such subjects should be treated per standard of care and followed till resolution.)
- The subject has endometrial thickness of ≥ 5 mm as measured by transvaginal ultrasound at Week 12, assessed centrally (subject with insufficient imaging data will have repeat transvaginal ultrasound)
- The subject has an abnormal endometrial biopsy result at Week 12, as assessed by the endometrial biopsy adjudication committee.
- The subject has endometrial thickness of ≥ 5 mm as measured by transvaginal ultrasound conducted at any time during the study based on investigator's judgement. (The images may be requested for central assessment.)
- The subject has an abnormal result from an endometrial biopsy conducted at any time during the study based on Investigator's judgement. (The biopsy report or slides may be requested for central assessment)
- Continuing the subject in the study off treatment would be detrimental to the subject's safety in the opinion of the Investigator

If a subject is discontinued prematurely from the study, the date the subject is withdrawn from the study and the reason for withdrawal will be recorded on the eCRF.

In case of discontinuation from study, the end of treatment (EOT) visit assessments should be performed, as far as possible (Sections 5.2.1.3 and 5.2.2) and any unresolved AEs or SAEs will be followed up according to Section 8.10.

The Investigator must make every effort to contact the subject to review all AEs. In the event that a subject discontinues from the study at any given time, the reason for discontinuation must be fully documented in the source documents and the eCRF. The Investigator and or site personnel will document the AEs and any other assessments in

the source documents and will make every effort to complete all required EOS assessments.

4.6 Study completion criteria

The study will be completed by the Sponsor when approximately 100 subjects complete a 52-week open-label treatment period and 30-day follow-up. Further treatment of study drug will not be allowed. At the completion of the study all subjects will be required to have EOT visit assessments within the defined visit window. All subjects will be followed for 30 days for AEs, and unresolved AEs or SAEs will be followed up according to Section 8.10.

4.7 Study stopping criteria

The study may be terminated by the Sponsor at any time upon becoming aware of data that could compromise the safety and/or wellbeing of subject or for any other reason it deems appropriate.

4.8 Lifestyle restrictions

Subjects must adhere to the following restrictions:

4.8.1 Alcohol restrictions

Subjects are prohibited from excessive consumption of drink and of food containing alcohol (>2 units* per day) at all times from Visit 1 through the Follow-up visit.

*Note: 1 unit of alcohol is equivalent to 8 g of pure alcohol.

4.8.2 Caffeine and xanthines

Subjects should avoid excessive consumption or an increase in consumption from Visit 1 of food or drink containing caffeine and methylxanthine (e.g., coffee, tea, cola, energy drinks, or chocolates) at all times from Visit 1 through the Follow-up visit. (Increased xanthines intake can interfere with assessment of sleep quality)

4.8.3 Contraception

Women of childbearing potential are excluded from this study; therefore, contraception is not required.

4.8.4 Diet

Subjects will be required to fast (except for water) for 6 hours after dosing at the night prior to Visit 1.

5 STUDY PLAN

Study assessments are summarised in the Time and events schedule (Table 1).

Table 1 Schedule of Assessments

Study Period	Open-label extension						Follow-up
Visit Number	Visit 1 ¹	Visit 2	Visit 3	Visit 4	Visit 5	Visit 6 (EOT)	Visit 7 (EOS)
Study Week ²	Week 12 ³	Week 20	Week 28	Week 40	Week 52	Week 64 ⁴	Week 68 ⁵
Study Day ±Window ²	Day 85 ±3	Day 141 ±7	Day 197 ±7	Day 281 ±7	Day 365 ±7	Day 448 ±7	Day 476 ±7
Informed consent	X						
Inclusion/exclusion criteria	X						
Physical examination ⁶	X	X	X	X	X	X	
Breast examination	X						X
Body weight	X			X			X
Vital signs ⁷	X	X	X	X	X	X	
12-lead ECG	X			X			X
Routine lab tests	X	X	X	X	X	X	
Transvaginal ultrasound ⁸	X						X
Endometrial biopsy ⁸	X						X
Reproductive hormones ⁹	X						X
PHQ-8 and GAD7	X		X				X
VMS diary	↔						
MENQOL	X		X			X	
Dispensing MT-8554 ¹⁰	X	X	X	X	X		
Drug accountability	X	X	X	X	X	X	
Adverse events	↔						
Concomitant medication	↔						
Compliance █ Calls to Subjects ¹¹	↔						

Abbreviations: ECG=Electrocardiogram; EOS=End of Study; EOT=End of Treatment Visit; GAD7=Generalized Anxiety Disorder-7 Questionnaire; MENQOL=Menopause Specific Quality of Life; PHQ-8=Eight-Item Patient Health Questionnaire; VMS=vasomotor symptoms.

1. Visit 7 (Week 12) of Study MT-8554-A01 will be considered Visit 1 of Study MT-8554-A02.
2. Study weeks and study days are in reference to the randomization performed on Day 1 in Study MT-8554-A01.
3. Assessments already carried out at Week 12 of Study MT-8554-A01 will not be repeated.
4. The EOT should be performed for subjects who complete treatment as well as those who withdraw from the study early.
5. The Follow-up visit, EOS, will be conducted by phone 30 days after the EOT visit for subjects who complete as well as those who withdraw early from the study.
6. Physical examination (abdominal, cardiovascular, general appearance, respiratory, and other) will be performed.
7. Vital signs (including sitting blood pressure, pulse rate, and tympanic body temperature) will be measured at all visits.

8. Transvaginal ultrasound and endometrial biopsy to be performed only on subjects who have a uterus. Pelvic examination will be performed only with endometrial biopsy.
9. Luteinizing hormone (LH), follicle stimulating hormone (FSH) and estradiol (E2) will be measured.
10. Subjects will receive 5 mg* of MT-8554 once daily. Investigators should instruct subjects to administer dose at least 2 hours after starting the evening meal and approximately 30 minutes before bedtime.
*Note: Based upon the results of Study MT-8554-A01, the dose is changed from 10 mg to 5 mg because participating subjects will no longer derive potential clinical benefit from receiving 10 mg dose. All participating subjects who reconsent to continue the study will receive MT-8554 5 mg.
11. Site staff will make periodic calls to the subjects at a minimum of every 4 weeks where no in-clinic visits occur, to confirm compliance with daily VMS diary data entry [REDACTED]

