5.2.1.2 Visits 2 to 5 (Treatment period, Weeks 20, 28, 40, and 52)

Subjects will attend visits every 8 weeks between Visits 1 and 3 (Weeks 12, 20, and 28) and every 12 weeks between Visits 3 and 6 (Weeks 28, 40, 52, and 64). The following assessments will be performed (refer to Table 1 for further details):

- Physical examination (see Section 6.5.1)
- Body weight (Visit 4 only)
- Vital signs (including sitting blood pressure, pulse rate, and tympanic body temperature)
- 12-lead ECG (Visit 4 only)
- Routine laboratory evaluations (hematology, biochemistry, coagulation, and urinalysis)
- PHQ-8 and GAD7 (Visit 3 only)
- MENQOL (Visit 3 only)
- Review VMS diary (re-educate subject if necessary)
- Dispensing MT-8554 (Visits 2 to 5 only)
- Drug Accountability
- AE and concomitant medication recording.
- Diary compliance [REDACTED] reminder

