5.2.1.3 Visit 6: EOT (Week 64 or early termination)

Subjects will attend the last visit of the treatment period and the following assessments will be performed (refer to Table 1 for further details):

- Physical examination (see Section 6.5.1)
- Breast examination
- Body weight
- Vital signs (including sitting blood pressure, pulse rate, and tympanic body temperature)
- 12-lead ECG
- Routine laboratory evaluations (hematology, biochemistry, coagulation, and urinalysis)
- Transvaginal ultrasound and Endometrial biopsy (for subjects with a uterus)
- Reproductive hormone assessments: E2, LH, and FSH
- PHQ-8 and GAD7
- MENQOL
- VMS diary collection
- Drug Accountability
- AE and concomitant medication recording.

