5.2.2 Follow-up

5.2.2.1 Visit 7: Follow-up Visit (FU, Week 68 or 4 weeks after early termination)

Subjects who complete the study (or subjects who withdraw from treatment early) will be telephoned by the Investigator (or designee) 30 days after EOT, for a Follow-up visit. Information on any new AEs, follow-up on existing AEs, and prior/concomitant medication will be recorded.

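### Women who stop drug but stay on study may have their only scheduled post-baseline endometrial assessment months off drug, and the SAP tables do not separate these results

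*Protocol*

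**What the plan says.** **When the EOT visit happens.** Protocol Table 1, footnote 4: "The EOT should be performed for subjects who complete treatment as well as those who withdraw from the study early". Footnote 5 sets the follow-up call 30 days later, "for subjects who complete as well as those who withdraw early from the study". Section 4.5.2 uses the same trigger: "In case of discontinuation from study, the end of treatment (EOT) visit assessments should be performed, as far as possible (Sections 5.2.1.3 and 5.2.2".

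**What happens when drug stops.** Section 4.5.1 handles this separately. For a woman who will not resume, "every effort should be made to continue the subject on study, e.g., attending study visits and carrying out study procedures through to the final visit". It sets no assessment at the last dose, but it does require dates: "The Suspension interval (start and end dates of suspension) and reason for suspending treatment must be recorded in source documents", and also in the eCRF.

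**Text that points the other way.** Section 5.2.2.1: "Subjects who complete the study (or subjects who withdraw from treatment early) will be telephoned by the Investigator (or designee) 30 days after EOT". Section 5.2.1.3 is headed "Visit 6: EOT (Week 64 or early termination", and the protocol does not define early termination.

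**Schedule after baseline.** Sections 6.5.5 and 6.5.6 place ultrasound and biopsy only at Week 64 or early termination. For ECG, section 5.2.1.2 gives "12-lead ECG (Visit 4 only", and section 5.2.1.3 adds one at Visit 6.

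**SAP.** Section 8.2.7.1 summarises thickness by visit. Section 8.2.7.2 summarises biopsy by visit and adds a shift table to Week 64 or EOT. Section 8.2.4 summarises ECG by scheduled visit and adds shift tables to EOT or early discontinuation. None sets a condition on the last dose. Section 7.2, Table 3, assigns analysis visits by study day and leaves unscheduled visits out of the derivation.

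**The concern.** Endometrial safety and ECG are among the primary safety endpoints. A reader of the Week 64 or EOT column will take it as the state at the end of about a year on drug. If some of those women took their last dose months earlier, a normal result fits two accounts: no effect on drug, or an effect that resolved after stopping. The documents give no time for endometrial change to reverse, so the tables cannot tell these apart.

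The exposure summary does not reveal the gap. SAP 7.3.1.4 runs duration of exposure to the EOT or withdrawal visit and ignores interruptions. Cumulative dosing days do subtract missed days, but no endometrial or ECG table uses them. An unscheduled scan at drug stop would not appear in the by-visit tables either.

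The Table 3 issue is separate and concerns women who leave the study early. Their EOT scan may be soon after the last dose. In the by-visit tables it is nevertheless filed under a week at which no scan is scheduled, or under no week at all.

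**Working it through.** **Inputs.** Nominal days and windows from Protocol Table 1: Visit 1 Day 85 ±3, Visit 2 Day 141 ±7, Visit 3 Day 197 ±7, Visit 4 Day 281 ±7, Visit 5 Day 365 ±7, Visit 6 Day 448 ±7. Analysis windows are from SAP Table 3. The extracted Table 1 shows some EOT marks under Visit 7, so the placement at Visit 6 is taken from section 5.2.1.3.

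**Step 1: the plan's own figure.** Treatment period = 448 − 85 = 363 days; 363 / 7 = 51.9 weeks, against the stated 52 weeks (364 days). It reproduces.

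**Step 2: days off drug at an on-schedule Visit 6** = 448 − day of last dose.

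| Last dose at | Days | Weeks |
|---|---|---|
| Visit 5 | 448 − 365 = 83 | 11.9 |
| Visit 4 | 448 − 281 = 167 | 23.9 |
| Visit 3 | 448 − 197 = 251 | 35.9 |
| Visit 2 | 448 − 141 = 307 | 43.9 |
| Visit 1 (one dose) | 448 − 85 = 363 | 51.9 |

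With protocol windows at both ends, the shortest gap is (448 − 7) − (365 + 7) = 441 − 372 = 69 days. The longest is (448 + 7) − (85 − 3) = 455 − 82 = 373 days.

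**Step 3: an early Visit 6.** SAP Table 3 counts Day 408 to 462 as Week 64. A last dose on Day 365 with a visit on Day 408 gives 408 − 365 = 43 days (6.1 weeks).

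**Step 4: the off-drug limit.** The documents give none, so three are tried. With Visit 6 on Day 448, a result is beyond the limit if the last dose was before:
- 14 days: 448 − 14 = Day 434
- 30 days: 448 − 30 = Day 418
- 60 days: 448 − 60 = Day 388

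Within the protocol windows, every stop by Visit 5 is beyond all three, since 69 > 60. In the Step 3 case it is beyond 14 and 30 days but inside 60, since 43 < 60.

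**Step 5: the Visit 4 ECG.** A last dose at Visit 3, 2 or 1 puts it 281 − 197 = 84, 281 − 141 = 140 or 281 − 85 = 196 days off drug. Both scheduled post-baseline ECGs are then off drug. A woman who stops after Visit 4 has one on-drug ECG.

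**Step 6: exposure.** A woman who stops at Visit 2 and stays to Day 448 has 448 − 85 = 363 days of exposure by the SAP formula, of which 141 − 85 = 56 were on drug (56 / 363 = 15%).

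**Step 7: Table 3 labels for an EOT visit at early study withdrawal.**
- Day 113 to 407 falls in the Week 20, 28, 40 and 52 windows.
- Day 86 to 112 (112 − 86 + 1 = 27 days) falls in none.

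**Not computable.** The documents do not give the number of women who stop for good, stay on study, have a uterus and meet no withdrawal criterion.

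**The case against.** The strongest objection is that the late assessment is not certain. Early termination is undefined and EOT means end of treatment. Section 5.2.2.1 ties the call after EOT to withdrawal from treatment. Section 3.1 times the follow-up call from the end of the treatment period. Section 7.1.2 has all drug returned at Visit 6, while section 7.1.6 allows return when treatment is discontinued. A site could reasonably hold the EOT visit at drug stop. This stands: footnotes 4 and 5 with sections 4.5.1 and 4.5.2 favour the later timing but do not settle it for every site.

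The gap can also be shorter than the nominal figures. The sponsor may close the study at about 100 completers, with EOT assessments for all subjects (section 4.6), and Step 3 shows a 43-day case. This stands as well.

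Safeguards exist. Unexplained bleeding or a significant breast finding leads to referral (4.5.1). A thickness of 5 mm or more, or an abnormal biopsy, leads to withdrawal (4.5.2). Endometrial, ECG and study-medication data are all listed, so off-drug results can be found by hand. These protect individual women and allow manual checking, but they do not separate the results in the tables.

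The ECG and biopsy shift tables already run to EOT, so the Table 3 problem is chiefly one for the by-visit ultrasound tables. That limit is accepted.

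Finally, the study is open-label and descriptive, and its importance here turns on elimination and reversal times that are not available; non-clinical and clinical background is redacted. This keeps the point modest. It does not remove it, because the table labels can be corrected without knowing those times.

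**Conclusion.** The concern holds in a limited form. On the reading that footnotes 4 and 5 and sections 4.5.1 and 4.5.2 favour, a woman with a uterus who stops by Week 52 and stays on study may have her only scheduled post-baseline ultrasound and biopsy, and her closing ECG, 83 to 363 days off drug at a nominal Week 64 visit (69 to 373 with the protocol windows). The gap is less if the visit is early or the study closes. The SAP puts these results together with on-drug results. The Table 3 labelling fault is certain on the text, but confined mainly to by-visit tables.

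A reader might infer more in three ways, and the documents do not support any of them:
- **That every woman who stops drug and stays is assessed late.** The undefined term and section 5.2.2.1 leave room for EOT at drug stop.
- **That the late results hide endometrial or cardiac harm.** No reversal time and no count of affected women is given; the tables are uninformative on this point, not shown to be wrong.
- **That following women off drug to Week 64 is itself a fault.** It is legitimate safety follow-up. The fault lies in how the results are tabulated.

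The off-drug limit is an assumption. Adverse events, routine laboratory tests and vital signs do not depend on Visit 6.

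**What to change.** Two SAP changes before database lock:

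1. In 8.2.4 and 8.2.7, and in 8.2.2 for reproductive hormones, derive days since last dose from the suspension and stop dates. Show EOT ultrasound, biopsy, hormone and ECG results beyond a stated limit in a separate row. Thirty days would serve as an example; it is an assumption to be justified by the sponsor.
2. In 7.2, give EOT and early-discontinuation assessments their own analysis row outside the Table 3 windows.

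The cost is one derived variable and two table rows. Suspension dates (Protocol 4.5.1) and dosing departures (Protocol 7.2.1) are already recorded, and SAP 7.3.1.4 already counts missed days. No new data are needed and no Week 64 result is lost.

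Two protocol edits may suggest themselves but are not recommended here. Rewording section 5.2.2.1 to match footnotes 4 and 5 would entrench the late assessment. Moving the EOT set to the time of permanent drug discontinuation is a trade-off: it gives a result nearer the last dose but gives up the off-drug Week 64 biopsy. It would also need changes to footnote 4 and sections 4.5.1 and 4.5.2.
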